g) *Impact of Particular Medication on Success of Weight Loss Intervention*: Preliminary analyses of the data from our current Merit Review Study, using a mixed general linear model shows that there are significant differences in the degree to which patients on different medications profit from our Lifestyle Balance Program ($F(5,7220)=15.06, p<.01$): patients on quetiapine, olanzapine and fluphenazine profit from the program, while the weight gain in patients on clozapine and risperidone does not appear to respond to the training program. These results are very preliminary due to the small number of patients in each of these patient subgroups at the moment.

h) *Impact of a Multi-Modal Approach*: The preliminary data analyses suggest that this intervention has an effect beyond what a pure exercise program can provide. Patients who reported at the baseline measurement that they were already exercising showed the same effect of the intervention as patients who had reported that they were not exercising (Test for the difference between these groups: $F(1,862)=0.03, p=.86$) (56).

3. Preliminary Conclusions from the Current Study: Though our study is not complete, we have excellent interim data that demonstrates that the Lifestyles Balance program, adopted from the DPP and administered for a year has positive impact. Even in the preliminary sample, we show significant positive impact on measures of the patients' weight, BMI, metabolic syndrome, and measures of cardiovascular disease risk factors. Other, more nuanced measures of physical and mental health also show sizable positive changes; these changes are not large enough to be detected in the preliminary, but the final sample as projected will provide sufficient power for them. We believe these changes in a population challenged with severe mental illness (and a significant proportion with a history of substance abuse) are quite encouraging.

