3. Repeated measures analyses: We propose to longitudinal (repeated measures) analyses to maximize the additional power we gain by observing the same subjects across 12 months.. Repeated measures analyses permit contrasts at each time point, and also describe and compare trajectories of change (trends), speed and durability of effects. We will also conduct separate cross-sectional to provide outcome data for ongoing safety review, interim progress reports, study oversight and conduct.

The primary design for longitudinal (repeated measures) analyses of continuous outcome scales will be a 2-group (treatment) mixed general linear model of timepoints nested within participants. This is very general linear model that permits flexibility in specifying the nature of the covariances among the dependent measures, allows time-dependent, within and between subject covariates, and permits incomplete (i.e., missing) data. Analyses of trends across the monthly assessments will be done using growth curve model within the mixed model analysis of covariance design with repeated measures described above. We propose to model a linear trend of time unless inspection clearly suggests nonlinearity. By fitting a slope over time (and intercept) for each participant who has baseline and at least one other measure, this method makes good use of all the data, and is robust even if some of the some measures are missing. The use of the mixed general linear model for all cross-sectional and linear hypotheses ensures that results will be comparable across different analyses and provide a framework to include group, person and time-specific covariates if it becomes necessary. The preliminary analyses have shown that this analysis strategy provides meaningful results even with partial data and suggests that we will exceed the originally projected power.**4. Stratification:** Randomization will be stratified by type of antipsychotic and presence of mood stabilizer medication (e.g., depakote, lithium) to assure balance on olanzapine and clozapine by randomizing within three strata – olanzapine, clozapine, and all other antipsychotics -- using three separate randomization lists. Because such stratification can adversely affect statistical power by creating artificially comparable (and heterogeneous) groups, two dummy variables coding olanzapine and clozapine at baseline will be included in all analyses as covariates.

4. Statistical Plans:

Primary Hypotheses:

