It provides valid statistics even in cases where there are more potential predictors than observations, and allows us to include all demographic, psychosocial, psychiatric and medical data known at baseline as potential predictors. The results of this analysis will suggest which patients are most likely to profit from further interventions, and it will also characterize the most at risk patients.

c) Subjects will continue to give meaningful, informed consent to participate throughout the study. They will see no significant decrease in their score on the informed consent quiz given every 6 months.

Analysis plan: A general linear model (GLM): ANOVA will be performed to compare the informed quizzes score results at 0, 6, and 12 months during the subjects' participation in the study.

5. Power Analysis: All calculations are based assuming a conventional medium effect size ($f=.25$, Cohen 1988); and a two-tailed alpha set at 0.05. Tuomilehto et al. estimated the SD of weight loss at roughly 5 kg across several treatment conditions (lifestyle changes vs. control) (76). A medium effect would thus translate into a group difference of about 2.5 kg or about 5.5 pounds. With an enrollment of $N=120$ and an estimated attrition rate of 45% we expect that at least 66 subjects will provide complete the study and provide 4 data points. The power analyses below are based on a sample size of $N=66$, i.e. this is a very conservative estimate due to the fact that the mixed linear model allows us to include cases with missing values in the analyses and that while they don't provide as much information as complete cases they still provide some information and will increase power. For the between-group comparisons, $N=66$ yields power=.7199 for main differences between groups if we assume that the within subject correlation is $r=.50$. Power to test for the difference in outcome trajectories of time – our main outcome variable is 0.99, and even if the effect is as small as $f=0.15$ we will have sufficient power to distinguish between the trajectories of the two treatment groups (power=0.83) insuring that we will get significant, insuring that we Preliminary data analyses shows that these assumptions are quite conservative and that effect sizes seem to be slightly larger than projected, suggesting that the final power will exceed the estimates presented here.

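### No stratum-by-time term is specified, so the olanzapine and clozapine dummies, if entered as ordinary covariates, do almost nothing for the trajectory test that the plan calls its main outcome

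*Combined protocol and SAP*

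**What the plan says.** The Stratification paragraph, which follows V.N.3 (Repeated measures analyses), sets up three randomization lists: olanzapine, clozapine and all other antipsychotics. It warns that stratifying can reduce power and, for that reason, states that "two dummy variables coding olanzapine and clozapine at baseline will be included in all analyses as covariates". It does not say whether the dummies also interact with time.

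The analysis plan under the primary hypotheses (V.N, Statistical Plans) uses a mixed linear model with four assessments as repeated outcomes: baseline, 8 weeks, 6 months and 12 months. The growth-curve option there gives each treatment group an intercept and a slope as fixed effects and each patient a random intercept and slope. No stratum slope is listed.

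The Power Analysis (V.N.5) reports "Power to test for the difference in outcome trajectories of time" and calls this the main outcome variable. It also says that "even if the effect is as small as $f=0.15$ we will have sufficient power". None of its calculations involves the strata.

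On drug and response, item g of the Preliminary Results (IV.E.2) reports that "there are significant differences in the degree to which patients on different medications profit from our Lifestyle Balance Program", and calls the result very preliminary.

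**The concern.** The dummies are there to protect power. Whether they can do so depends on how they enter the model, and the plan leaves that open. When baseline is part of the outcome vector, a covariate that is constant over time moves a patient's whole curve up or down. It carries no information on how the curve bends, and the group-by-time test is about the bend.

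If weight course over 12 months differs by drug stratum, that variation stays in the error term of the trajectory test. The treatment groups have been balanced on drug, but the analysis does not take credit for it. The standard error is then somewhat larger than it need be and the test slightly conservative. What is at stake is some precision in a trial that expects 66 completers, not the validity of the result.

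**Working it through.** **1. Inputs from the documents.** V.N.5: "a two-tailed alpha set at 0.05"; f = 0.25 for planning and f = 0.15 as the smaller alternative; N = 66 completers from 120 enrolled with 45% attrition; m = 4 visits; within-subject correlation r = 0.50. It cites a study that "estimated the SD of weight loss at roughly 5 kg".

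**2. The plan's own powers reproduce.** Repeated-measures ANOVA, noncentral F:
- Between groups: λ = N f² m / [1 + (m−1) r] = 66 × 0.0625 × 4 / 2.5 = 6.6, df 1 and 64. Power 0.716 (stated 0.7199).
- Group-by-time, f = 0.25: λ = N f² m / (1 − r) = 66 × 0.0625 × 4 / 0.5 = 33, df 3 and 192. Power 0.999 (stated 0.99).
- Group-by-time, f = 0.15: λ = 66 × 0.0225 × 4 / 0.5 = 11.88, same df. Power 0.828 (stated 0.83).

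**3. Why main-effect dummies drop out.** Let patient i have outcome vector y_i with covariance Σ, and let the dummies add the same shift x_i′γ at every visit. Any contrast c′y_i with c′1 = 0 (a change between visits) has an expectation free of γ. The remaining component, 1′Σ⁻¹y_i, is uncorrelated with every such contrast because c′ΣΣ⁻¹1 = c′1 = 0. It has its own free intercept and group effect, so it tells nothing about change. The group-by-time estimate therefore comes from the contrasts alone, with or without the dummies. This needs complete visits and a linear model.

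**4. Simulation check.** Linear mixed model with known covariance, 400 trials of N = 120 per setting. Assumed, because the documents give none of these: 1:1 allocation, 25% olanzapine, 10% clozapine, stratum slopes of +3 and −3 kg per 12 months. Change in the group-by-time estimate when main-effect dummies are added:

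| Setting | Mean absolute change | Maximum |
|---|---|---|
| Complete data | 0.000 kg | 0.000 kg |
| 45% dropout, unrelated to stratum | 0.02 kg | 0.09–0.11 kg |
| Dropout differing by stratum and arm | 0.06 kg | 0.16 kg |

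Under dropout the standard error is about 0.6 to 0.9 kg, so these shifts are negligible.

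**5. What stratum-by-visit terms could gain.** Suppose they remove a share R of the error variance in the trajectory test. Then λ becomes λ/(1 − R), and the denominator df falls by six to 186.

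| R (assumed) | λ at f = 0.15 | Power at f = 0.15 | Power at f = 0.25 |
|---|---|---|---|
| 0 | 11.88 | 0.828 | 0.999 |
| 5% | 12.51 | 0.848 | above 0.999 |
| 10% | 13.20 | 0.869 | above 0.999 |
| 20% | 14.85 | 0.908 | above 0.999 |

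The R = 0 row shows that the six parameters cost almost nothing when strata change alike.

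**6. What such an R would require.** As a rough guide, take strata of 65/25/10% and a within-stratum SD of 12-month change of 5 kg (both assumed). If olanzapine and clozapine each differ from the rest by d kg, the between-stratum variance is 0.35d² − (0.35d)² = 0.2275d².
- d = 1: 0.23, a share of 0.23/25.23 = 0.9%.
- d = 3: 2.05, a share of 2.05/27.05 = 7.6%; the standard error without the terms is √(27.05/25) = 1.04 times as large.

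This is for month-12 change and only approximates the share in the four-visit test.

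**The case against.** **The text says covariates, not main effects only.** That is correct. V.N.3 adds that the model can take time-dependent covariates, and time-specific ones if they become necessary. A reader might infer that the plan fixes a main-effects model; it does not. But no stratum-by-time term is named, and the growth model's listed fixed effects include none. Main effects are the natural reading, and the open point is the one that decides whether the adjustment helps.

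**The identity is exact only for complete data in a linear model.** This stands. The plan expects 45% attrition and uses a logistic link for the lifestyle-change hypothesis, a case not checked here. In the linear model the departure under dropout is too small to matter.

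**The stratified design is still used.** A reader might infer that it is wasted. Stratified randomization itself protects balance on drug, and the dummies act on the between-group main effect, for which the plan also reports power. If the knowledge hypothesis is analyzed as change scores, the dummies act on change directly.

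**The documents do not show that strata differ in change.** This stands too. Section II.C ranks drugs by weight-gain liability without figures in kg, and eligible patients have already gained weight or reached a BMI of 25. Item g of the Preliminary Results concerns drug-by-program response, which a stratum-by-time term common to both arms does not model. It also cuts across the strata: quetiapine, fluphenazine and risperidone all fall in the third stratum although their reported responses differ.

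**Planned power is not lost.** A reader might infer a shortfall from a completers' comparison of month-12 change, where power for 2.5 kg with SD 5 kg and N = 66 is only about 0.53. That is a different test. If the cited 5 kg is the total SD, any stratum variation is already inside it, and stratum-by-time terms would be a bonus.

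**Conclusion.** The point holds as a free improvement, not as a demonstrated error. No stratum-by-time term is specified. If the dummies enter as ordinary covariates, they have no effect on the linear group-by-time test with complete data and a negligible one under the planned attrition. The adjustment then fails to serve its stated purpose for the test that the plan calls its main outcome.

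The consequence is small to moderate and conservative. It ranges from essentially nothing, if strata change alike, to about 2 to 8 percentage points of power at f = 0.15 under an assumed 5% to 20% reduction in error variance. At f = 0.25 power is above 0.99 either way. The algebra rests on the linear model with baseline among the outcomes; the size rests on stratum shares and differences that the documents do not give.

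A reader might go further and infer inflated type I error, a biased treatment effect or an underpowered trial. None of these follows: the plan's stated powers reproduce, and any error in the test is in the conservative direction.

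**What to change.** In the Stratification paragraph and in the analysis plan for the primary hypotheses, state that:
- in the linear repeated-measures models, the two stratum dummies enter together with stratum-by-visit terms (2 dummies × 3 post-baseline visits = 6 extra parameters);
- in the linear growth model, they enter with stratum-by-time terms (2 extra parameters);
- where change scores are analyzed, or post-baseline values with baseline as a covariate, the dummies stay as main effects, because there they act on the outcome of interest directly.

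The cost is one or two sentences. Strata are known at randomization, so no new data are needed, and sample size and conduct do not change.

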Treatment Adherence Log	5	C	X		X				X							X
URICA Motivational Scale	10	C	X						X							X
Vitals: Weight, BMI, Waist, %Fat	10	C	X	X	X	X	X	X	X	X	X	X	X	X	X	X
Lifestyle Balance Classes	60	RD	X	X	X											
Lifestyle Balance Booster classes	60	RD				X	X	X	X	X	X	X	X	X	X	X
Personal Goal Sheet	10	RD	X	X	X	X	X	X	X	X	X	X	X	X	X	X
Eating Behavior & Exercise Adherence – additional interventions	2	RD		X	X	X	X	X	X	X	X	X	X	X	X	X
Caregiver dietary Information Session	60	RD	X			X			X			X				X
Food and Exercise Diary	15	RD	X	X	X	X	X	X	X	X	X	X	X	X	X	X
Exercise Tolerance Test	120	C	X													
Electrocardiogram	15	C	X													

Example Schedule for Lifestyle Balance Classes and Exercise Opportunities at West Los Angeles Site

Day of Week	Mon	Tue	Weds	Thurs	Fri
AM Class	Cohort 1	Cohort 2	Cohort 3	Cohort 4	Cohort 5
PM Class	Booster	Booster	Booster	Booster	Booster
Day of Week	Monday	Tuesday	Wednesday	Thursday	Friday
Exercise Options offered at PRRC:	Walking Group 11:00am Yoga 1:00pm	Physical Fitness 8:00am Yoga 1:00pm Golfing 2:00pm	Yoga 2:00pm	Thai Chi 9:00am Field Trip 10:00am (eg farmers market, museum)	Yoga 1:00pm

				walking)	
Exercise option Rehab wellness clinic	Daily available stationary bicycle and weight lifting	Daily available stationary bicycle and weight lifting	Daily available stationary bicycle and weight lifting	Daily available bicycle and weight lifting	Daily available bicycle and weight lifting

G. Study Assessments:

1. Screening and General Medical Procedures: The process of obtaining informed consent will culminate in a quiz on the details of the project and participating in research, which is repeated at 6 and 12 months. During the first visit, patients will have a comprehensive physical exam and psychiatric interview. An electrocardiogram and demographics will be recorded. Framingham risk assessment for cardiovascular disease will be calculated and repeated at the end of the study. Routine vital signs, blood pressure, and pulse will be measured at each visit. Patients at high risk for cardiovascular disease and/or current symptoms of angina may need referral for an exercise tolerance test before embarking upon the exercise component of this behavioral weight loss program. [name], our co-investigator in charge of the outpatient rehabilitation medicine department, has agreed to assist us with expediting exercise tolerance tests for patients wishing to participate in exercise as part of their weight loss plan.

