a) SMI patients with antipsychotic associated obesity who participate in a behavioral intervention that includes classes on Lifestyle Balance will gain more knowledge (i.e., greater change scores on before/after survey test instrument) about general health issues (e.g., nutrition, importance of exercise.) than a control group receiving “usual psychiatric care”.

b) SMI patients with antipsychotic associated obesity who participate in a behavioral intervention program will achieve better cardiovascular (e.g., sustained weight loss, better glucose tolerance, improved lipid profiles, and improvement in other biological measures, e.g. insulin and c-reactive protein) and mental health (e.g., improvements in general measures of psychopathology, subjective quality of life, etc) outcomes than the control group. A larger proportion of patients who take the Lifestyle Balance classes will actually make lifestyle

changes (objectively measured by food and exercise diaries) than patients in the usual care group given ordinary counseling.

c) A larger proportion of patients who take the Lifestyle Balance classes will actually make lifestyle changes (objectively measured by food and exercise diaries and exit interviews) than patients in the usual care group given ordinary counseling. Analysis plan: For all hypotheses concerning the effects of the treatment program use analysis of repeated measures using the assessments at baseline, 8 weeks, 6 months, and 12 months. These analyses will provide information about maintenance of treatment effects. We will use a mixed general linear model with timepoints nested within patients. For hypothesis (c) we will adapt the mixed general linear model to dichotomous data by using a logistic link function to model the likelihood of life style changes. We will include all patients with at least one post-baseline data point in the analysis to maximize power. We will also consider the appropriateness of linear growth curve mixed effects models, i.e., fitting an intercept and linear slope for each treatment group as fixed effects, and separate intercepts and linear slopes for each patient as random effects. Analyses of linear trends over time with a single df effect are often more powerful tests of differences in trends than multiple df profile contrasts across the separate time points.

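### The plan gives two conflicting sets of time points for weight and the other measures taken at every visit: four landmark visits, or the monthly assessments

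*Combined protocol and SAP*

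**What the plan says.** Two parts of section V.N describe the primary longitudinal analysis.

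- **V.N.3, Repeated measures analyses**, sets out a mixed general linear model as the primary design for continuous outcomes. It continues: "Analyses of trends across the monthly assessments will be done using growth curve model". Time is linear unless inspection clearly suggests otherwise. A slope is fitted for anyone with baseline and one further measure, and the method is recommended because it exploits all available data.
- **V.N.4, Statistical Plans, Primary Hypotheses**, directs that every hypothesis about the effect of the programme should "use analysis of repeated measures using the assessments at baseline, 8 weeks, 6 months, and 12 months". Linear growth curve models are only to be considered. Patients with at least one post-baseline data point are included.

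The Schedule of Events marks the row "Vitals: Weight, BMI, Waist, %Fat" at every visit, and V.G.2 (Weight Loss Measures) says the same in words. Power Analysis (V.N.5) assumes four data points per completer. Attrition (V.N.2) undertakes to seek full follow-up whatever the degree of participation, and to include every enrolled participant with any outcome data.

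**The concern.** Weight is the outcome on which V.N.5 scales its effect, and it is the most frequently measured. Two specifications for it leave the choice of visits, and of slope or 12-month difference, open until the data have been seen.

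If V.N.4 is followed literally, a patient lost to follow-up just after month 11 has five monthly weights (months 7 to 11) that never enter the model. One lost at week 7 has weekly weights on file but no post-baseline value at a landmark visit. V.N.4 relies on data being missing at random, and a lost patient's last weights are the observed data most relevant to that assumption. At 45% expected attrition, this concerns many patients.

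**Working it through.** **Inputs.** From V.N.5: N = 120, attrition 45%, 66 completers (120 × 0.55 = 66), 4 data points, f = 0.25, within-subject correlation 0.50, two-sided 5%. From the Schedule of Events: visit 0, visits 1–7, visit 8 and visits 9–18, so 1 + 7 + 1 + 10 = 19 weights. Not in the documents, so assumed: 1:1 allocation, a constant dropout hazard, and the covariances below.

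**1. The plan's power rests on four visits.**
- Between groups: λ = f²Nm/[1+(m−1)ρ] = 0.0625×66×4/2.5 = 6.6 on 1 and 64 df. Power is 0.716 (plan: 0.7199).
- Group by time: λ = f²Nm/(1−ρ) on 3 and 192 df. For f = 0.25, λ = 33.0 and power is 0.999 (plan: 0.99). For f = 0.15, λ = 11.88 and power is 0.828 (plan: 0.83).
- With m = 19 in the between-group formula, λ = 0.0625×66×19/10 = 7.84 and power is 0.787. The group-by-time figure is not extended to 19 visits, because f changes meaning for that term when visits are added.

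**2. Patients affected if only four visits are used.** Let S(t) = 0.55^(t/52), with t in weeks.
- No post-baseline value before week 8: 120×(1−S(8)) = 120×(1−0.912) = 10.5.
- No post-baseline value before week 1: 120×(1−S(1)) = 120×(1−0.989) = 1.4.
- Difference: about 9 randomized patients who have a weight after baseline but none at a landmark visit.
- Of the 54 expected dropouts, about 44 (81%) would have at least one weight later than their last landmark visit.

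**3. Precision.** Generalised least squares information, summed over dropout patterns with 60 per arm, comparing weeks 0, 8, 26 and 52 with all 19 visits. The 12-month contrast is change from baseline to week 52 with visit as a category. Power is for an effect set to give 80% with four visits.

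| Assumed covariance (standardised) | 12-month SE, 19 vs 4 visits | Variance ratio, 4 vs 19 | Power from 0.80 to | Linear slope variance ratio |
|---|---|---|---|---|
| Compound symmetry, 0.5 | 0.971 | 1.06 | 0.82 | 3.49 |
| Serial decay to 0.5 at week 52, 5% measurement error | 0.967 | 1.07 | 0.83 | 1.11 |
| Random intercept (0.55) and slope (0.45 per year), residual 0.10 | 0.944 | 1.12 | 0.84 | 1.42 |

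A second set on the kilogram scale (intercept SD 20 kg, residual SD 2–3 kg, slope or Brownian SD up to 4.5 kg, common baseline mean) gave 1.09 to 1.13 for the 12-month contrast. At its upper end the SE falls from 1.19 to 1.12 kg, and (1.19/1.12)² = 1.13. With complete data and 33 per arm, the 12-month change contrast gains nothing (ratio 1.00) under any of the three covariances in the table.

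**4. The visit set also moves a linear estimate.** Suppose the plan's 2.5 kg difference is reached in a straight line by a plateau week and then held. With complete data, the least-squares slope times 52 weeks gives:

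| Plateau | Four visits | Baseline, week 8 and monthly | All 19 |
|---|---|---|---|
| Week 8 | 1.75 kg | 1.21 kg | 1.78 kg |
| Week 26 | 2.51 kg | 2.38 kg | 2.86 kg |

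The spread is about 0.5 kg in each row, on a true 12-month difference of 2.5 kg. The shapes are illustrative, but weekly contact for two months followed by monthly contact makes some curvature plausible.

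**The case against.** A reader might infer that the primary analysis definitely uses only four visits and discards the rest. The documents do not support that. V.N.3 plans growth curves over the monthly assessments, and V.N.4 keeps such models open. V.N.3 also treats the earlier study's analysis as the same strategy. That weight test (IV.E.2) had 935 denominator df, more than the 123×4 = 492 observations that four visits from all randomized patients could give. The earlier visit schedule is not stated, so this is supporting evidence only.

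A reader might also infer that stopping the programme ends a patient's data. V.N.2 says follow-up will still be attempted, so the loss applies only to patients actually lost to follow-up. Their earlier landmark values stay in the likelihood, and V.N.2 would compare dropouts on trajectory and status at the last data point. The rule requiring one post-baseline value does not itself confine that value to the four visits; the exclusion follows only if the four visits define the data.

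Fixed landmark visits are a legitimate choice, and for the BPRS, CGI and Hamilton scales they are all that is scheduled. An unstructured covariance over 19 visits has 19×20/2 = 190 parameters for 120 patients with heavy attrition, so using every visit is not free.

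All of this stands. None of it says which text governs weight.

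**Conclusion.** The point holds as an unresolved conflict between V.N.3 and V.N.4 over measures taken at every visit. If the four-visit text governs, about 9 of 120 randomized patients with a post-baseline weight fall out of the weight analysis, contrary to V.N.2, and later weights of patients lost between landmarks go unused. Those counts assume a constant hazard, with the plan's 45% taken as loss to follow-up.

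The gain in precision for the 12-month contrast is modest: SE about 3 to 6% smaller, worth roughly 6 to 13% more patients, under the assumed covariances and dropout. It arises only because of dropout.

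The slope results might tempt a reader to claim a large gain. Their variance ratio runs from about 1.1 to 3.5 depending on a covariance the documents do not give, and it presumes a straight line, so it should not be a headline. The stronger reasons to act are the open choice of visits and estimand and the avoidable exclusions.

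**What to change.** In V.N.4, state that weight, BMI, waist and percent body fat are analysed with all scheduled visits in the mixed model. Time should not be forced to be linear (visit as a category or a prespecified curve). Name a structured covariance in advance, and make the between-arm difference at 12 months the single reported contrast. State that any post-baseline visit satisfies the inclusion rule for these measures.

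Keep the four visits for outcomes measured only then. Say also whether the month-9 laboratory values in the Schedule of Events enter the analysis, since they too fall outside the four visits. Amend V.N.3 so that its monthly, linear-trend wording agrees.

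The cost is a few sentences and no new data. The small downside is more covariance modelling, which a structured form keeps manageable. The power calculation can stay on four data points.
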